### 3. Subgroups for Secondary Analysis

1. Patients receiving chronic dialysis
2. Patients with history of chronic heart failure (as documented in past medical history)
3. Patients with qualifying SBP < 90 mmHG versus 90-100 mmHG at randomization

4. Patients age > 65 years of age
5. Patients with a clinically confirmed infection as a cause of hypotension at study enrollment (as assessed by the investigator using records available throughout hospitalization)
6. Patients with pneumonia as the etiology of sepsis
7. Stratification by SOFA score quartiles on enrollment
8. Patients enrolled in the ED (vs. wards or ICU)
9. Use of cardiac ultrasound or other hemodynamic monitoring techniques (yes or no; defined in Section 5.3)
10. Patient with a history of hypertension (as documented in past medical history or by the prescription of chronic medications)
11. Patients enrolled prior to and following the protocol change regarding required or optional use of the second liter of fluid infusion in the liberal treatment arm.

As per NIH guidelines we will also do secondary analysis by sex, ethnicity, and race.

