3.6.3 Process of Care Metrics

1. Total intravenous fluids administered over first 6 hours after randomization
2. The total amount of intravenous fluids or blood products of any type administered from pre-randomization to 6 hours after randomization.
3. Total intravenous fluids administered over 24 hours after randomization
4. The total amount of intravenous fluids or blood products of any type administered from pre-randomization to 24 hours after randomization.
5. Proportion receiving vasopressors and timing of vasopressor initiation within 24-hour study period

- a. Proportion of patients receiving vasopressors within 24 hours will be calculated. Additionally, among patients who received vasopressors, the duration of time elapsed from randomization until the time of initiation of vasopressor medications within 24-hour protocol period will be recorded.
6. Total fluids administered prior to initiation of vasopressors
 - a. This process of care metric will assess the amount of fluids administered prior to the first receipt of vasopressors. (patients on vasopressors prior to randomization excluded from this metric)

We will use a bedside flow-sheet as a data collection instrument to record fluid and vasopressor administration, with the indications for administration, during the 24-hour protocol period. This will detail the delivery of the study interventions and assess protocol compliance. The data will be reported to the protocol oversight committee (and disseminated to the sites as protocol compliance metrics) as aggregate per-arm data in a blinded fashion (e.g. descriptive numbers only without an “n” or any indication of outcome or clinical status). This will occur at the 100, 200, and 300 patient data completion marks as described in the feasibility evaluation phase (Section 8). After the feasibility evaluation phase, we will perform a simplified data collection of summary fluid and vasopressor administration during the 24-hour treatment period and the data will be distributed after the first 10 patients for any new site, and then quarterly, to allow treatment protocol adherence monitoring. Any site with deficient compliance and/or separation of treatment arms after the initial 10 patients or during the quarterly reports may receive re-education and/or be asked to cease enrollment.

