5.1 Restrictive Fluids Group (Early Vasopressors)

Restrictive Group Treatment Protocol

Once a patient is randomized to the restrictive fluids arm, the general approach will be to use vasopressors to treat hypotension as opposed to intravenous fluids. Maintenance fluids should not be used. Restoration of blood pressure and perfusion should be accomplished in accordance with the following protocol recommendations:

1. Initiate vasopressors (norepinephrine recommended first-line vasopressor) for MAP < 65 mmHg or SBP <90 mmHg
2. Titrate vasopressors to: 65 mmHg < MAP <75 mmHg
3. *"Rescue Fluids" are recommended, but not mandated, in 500 cc crystalloid boluses for any of the following:
 - a. Severe hypotension (SBP <70 mmHg or MAP <50 mmHg)
 - b. Refractory hypotension (MAP <65 mmHg) despite norepinephrine dose of at least 20 mcg/min or 0.25 mcg/kg/min or equivalent dose of another vasopressor (see Appendix E)
 - c. Lactate > 4 mmol/L and rising from previous lactate, after at least 2 hours of therapy, in patients with serial lactates measured in usual care practice
 - d. Sinus heart rate > 130 beats per minute for >15 minutes
 - e. Evidence of extreme volume depletion from hemodynamic monitoring (if performed) based on any of the following:
 - i. Maximal IVC diameter < 5mm; or

- ii. Empty left ventricle on echo (i.e. left-ventricular end-diastolic area index < 5.5 cm²/m² BSA) or
- iii. Substantial volume responsiveness defined as stroke volume increase > 30% in response to a passive leg raise, fluid challenge, or positive pressure breaths during passive ventilation)

*Rescue fluids may be administered at any time if the clinical team believes that it is in the best interest of the patient

4. Patients should be monitored for volume overload, and fluids may be halted or reduced for clinical evidence of *symptomatic left atrial hypertension based on a clinical diagnosis by the treating or study physician.
 - a. *Clinical features of symptomatic LA hypertension: signs and symptoms of fluid overload (or hydrostatic edema due to left atrial hypertension) include manifestations such as increased respiratory rate, increased use of accessory muscles of respiration, increased bilateral inspiratory crackles, increasing oxygen requirement, or pulmonary edema on chest x-ray likely cardiogenic in origin).
5. Return to care without study guidance for any of the following protocol endpoints:

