5.2 Liberal Fluids Group

Liberal Empiric Fluid Strategy

1. Initiate a 2000 cc crystalloid fluid infusion upon randomization (2000 cc to be complete within 180 minutes of randomization; clinician may extend infusion time at any point during the 2000 cc infusion if indicated for a given patient); monitor for signs of fluid overload
2. Clinical evaluation at the end of first 1000cc:
 - If blood pressure and heart rate have normalized (SBP ≥ 110 mmHg or MAP ≥ 70 mmHg and HR < 90 bpm) and clinical assessment is patient is volume replete, team

- may forego second liter and move to 500cc boluses based on fluid triggers (#5 below); otherwise continue with second 1000cc infusion
3. Maintenance fluids should not be used.
 4. Balanced crystalloid solution (such as lactated Ringers, Hartman's solution, Plasmalyte or Normosol) is recommended, normal saline is permitted.
 5. Subjects receive a 500cc crystalloid fluid bolus for any of the following fluid triggers:
 - a. SBP < 90 mmHg or MAP <65 mmHg
 - b. Lactate > 4 mmol/l and rising in patients with serial lactates measured as part of usual care practices
 - c. Reduced urine output (<30 cc/hour) for > 1 hour (except for ESRD patients)
 - d. Sinus heart rate > 110 beats per minute
 - e. Any measured/clinical assessment of volume status or volume responsiveness (e.g. echo, IVC measurement, CVP, etc) suggesting benefit from additional fluid (as defined by treating clinicians)
 - f. Receiving vasopressors to maintain SBP \geq 90 mmHg or MAP \geq 65 mmHg
 6. Patients should be monitored for volume overload, and fluids may be halted or reduced for clinical evidence of *symptomatic left atrial hypertension based on a clinical diagnosis by the treating or study physician.
 - a. *Clinical features of symptomatic LA hypertension: signs and symptoms of fluid overload (or hydrostatic edema due to left atrial hypertension) include manifestations such as increased respiratory rate, increased use of accessory muscles of respiration, increased bilateral inspiratory crackles, increasing oxygen requirement, or pulmonary edema on chest x-ray likely cardiogenic in origin).
 7. "Rescue vasopressors" recommended (in the form of norepinephrine infusion) for any of the following criteria:
 - a. SBP < 70 mmHg or MAP < 50 mmHg for at least 5 minutes)
 - b. Signs of volume overload (see above) with persistent hypotension/hypoperfusion
 - c. Lactate > 4 mmol/L and rising from previous lactate, after at least 2 hours of therapy

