5.3 The Use of Cardiac Ultrasound and Other Hemodynamic Monitoring Techniques

The use of advanced monitoring techniques, such as echocardiography, pulse contour analysis, bioimpedance and bioreactance, will be permitted but not mandated. If the clinician wishes to use these techniques, fluid administration should be titrated according to the CLOVERS study fluid protocol guidelines. In the restrictive group, clinical teams should refrain from adjusting treatment intervention outside the guidance provided whereby fluid boluses are administered only for the “Rescue Fluid” indications stated in the protocol (Section 5.1.c) unless the clinical team believes that alternative approaches would be in the best interest of the patient. In the fluid liberal group, we permit the clinician to use these techniques and allow for fluid boluses based on any provider-chosen metric of volume responsiveness.

6. Duration of the Protocol

The protocols are intended to run for 24 hours post randomization. Fluid management after 24 hours will be dictated solely by the clinical team.

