8.2 Compliance with Fluid Management Protocols

Compliance with the hemodynamic protocol instructions and the safety of the protocol will be monitored by the protocol oversight committee and DSMB. Detailed treatment data in regards to intravenous fluid administration, vasopressor use, vital signs, and the presence of protocol defined criteria for fluid and vasopressor administration will be collected hourly for the first 24 hours by the sites on a detailed flow sheet. We will assess protocol compliance (defined as following the protocol rules based on vital signs and actions) for the first 6 hours, and then randomly sample 4 other 1-hour time-points during the 24-hour treatment period. The compliance rate will be defined as the proportion of correct actions among the total actions performed; or $(\text{correct actions})/(\text{correct} + \text{incorrect actions}) \times 100$.

A “correct action” in the liberal group is defined as:

- a. Administration of the initial 2-liter fluid infusion within the first 180 minutes (if documented clinical assessment leads to a decision to administer less than two liters during the initial infusion or if the infusion time is deliberately lengthened, this is considered a correct action)
- b. Administration of a minimum 500cc fluid bolus when a “meets intervention criterion” is present
- c. Vasopressor use in the presence of a “rescue criterion”
- d. No fluid or vasopressor administration in the absence of a meets intervention criterion

An “incorrect action” in the liberal group is defined as:

- a. Failure to administer the initial 2-liter fluid infusion within the first 180 minutes (if clinical evaluation is that patient has normalized - fluids may stop and be considered a correct action).
- b. Failure to administer a 500cc fluid bolus when a “meets intervention criterion” is present and there is no contraindication (e.g. fluid overload or > 5 liters criteria already administered)
- c. Use of a vasopressor in the absence of a “rescue vasopressors recommended” criterion
NOTE: In both arms, fluids or vasopressors can be used at any time if the clinical team feels they are in the best interest of the patient. An incorrect action as defined in the protocol is not a protocol deviation but would be considered non-compliant for the purposes of compliance monitoring.

A “correct action” in the restrictive group is defined as:

- a. Initiation of vasopressors for SBP < 90mmHg and/or MAP <65mmHg within 60 minutes

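### SAP subgroup 9 (haemodynamic monitoring) has no time window or rule for 'yes', reads as care chosen after randomisation, and is tested as if it were a baseline factor

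*SAP*

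**What the plan says.** SAP section 3, item 9, lists the subgroup as "Use of cardiac ultrasound or other hemodynamic monitoring techniques (yes or no; defined in Section 5.3"). SAP section 5 is Statistical Methods and has no numbered subsection 5.3. The matching text is protocol 5.3, whose title is nearly the same as item 9. It says that techniques such as echocardiography and pulse contour analysis "will be permitted but not mandated", and continues: "If the clinician wishes to use these techniques, fluid administration should be titrated according to the CLOVERS study fluid protocol guidelines".

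The use made of a result then depends on the arm:

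- **Liberal arm.** Protocol 5.3 says "we permit the clinician to use these techniques and allow for fluid boluses based on any provider-chosen metric of volume responsiveness". Protocol 5.2 makes "Any measured/clinical assessment of volume status or volume responsiveness (e.g. echo, IVC measurement, CVP, etc") a trigger for a bolus when it suggests benefit.
- **Restrictive arm.** Protocol 5.1 lists among its rescue-fluid criteria "Evidence of extreme volume depletion from hemodynamic monitoring (if performed) based on any of the following". Protocol 5.3 asks teams to keep to the rescue criteria unless they judge otherwise for the patient.

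SAP section 5 (Secondary Analysis by Subgroups) adds subgroup and subgroup-by-treatment terms for every listed subgroup, at two-sided 0.05 with no multiplicity adjustment. It makes no exception for item 9.

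**The concern.** A subgroup analysis keeps the protection of randomisation only if assignment cannot change who belongs to the subgroup. Item 9 states no time point, and the section it appears to cite describes what clinicians may do once the arm is known. If teams in one arm tend to scan their sicker patients and teams in the other scan more evenly, monitored patients in the two arms are no longer alike. The contrast within them then mixes treatment with case mix.

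The result could be misread. A difference among monitored patients would look like evidence on monitoring-guided resuscitation when it might only reflect selection. Separately, two analysts could build different 'yes' groups (before randomisation, within 24 hours, whole stay; with or without CVP), and neither would depart from the SAP.

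**Working it through.** **Step 1: what the text fixes.** Protocol 5.3 partly answers which techniques count, by examples. It does not say when use counts or how much use makes a 'yes'. CVP is named as a volume assessment in protocol 5.2 but not in 5.3. Protocol 11.1 expects that more central lines may be placed in the restrictive arm, so if CVP counts, membership could follow assignment.

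The factor is absent from the background assessments (protocol 7.1) and the baseline characteristics (SAP 4). The type I error statement at the end of SAP section 5 concerns outcomes defined only in patients on study. It does not cover subgroup membership that assignment may alter.

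**Step 2: inputs for an illustration.** The documents give 2320 patients at 1:1 (1160 per arm), two-sided 0.05, and mortality of 15% against 10.5%. The usual fixed-sample two-proportion formula at 90% power gives 2 × 1153 = 2306, close to 2320. There is no planned figure for item 9. All monitoring rates and severity links below are assumptions.

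**Step 3: model, with no effect of arm on death.**

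- Severity S ~ N(0,1).
- logit P(death) = a + b·S, with b = 1 (0.5 for a weak link). The constant a is set so that overall mortality is 15%, or 12.75%, the mean of 15% and 10.5%.
- P(monitored | S) is logistic in S, with an arm-specific overall rate and slope.
- Mortality among the monitored = E[P(monitored|S)·P(death|S)] / E[P(monitored|S)]; likewise for the unmonitored.
- Bias is restrictive minus liberal. The false interaction is the monitored bias minus the unmonitored bias.

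**Step 4: one case in full.** Monitoring is 30% in each arm, with slope 0.5 (liberal) against 0.25 (restrictive), b = 1 and 15% mortality.

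- Monitored: 17.00% − 18.95% = −1.95 points.
- Unmonitored: 14.14% − 13.31% = +0.83 points.
- False interaction: −1.95 − 0.83 = −2.78 points.
- Cell sizes: 1160 × 0.3 = 348 and 1160 × 0.7 = 812.
- SE = √(0.1895·0.8105/348 + 0.1700·0.8300/348 + 0.1331·0.8669/812 + 0.1414·0.8586/812) = 3.37 points.
- Rejection ≈ Φ(2.78/3.37 − 1.96) + Φ(−2.78/3.37 − 1.96) = 0.131. Simulation of 10,000 trials gives 0.132.

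**Step 5: all cases.** Rejection is simulated (Monte Carlo SE at most 0.004). Bias is in points at 15% mortality.

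| Liberal vs restrictive (rate/slope) | Rejection at 15%, 12.75% | Bias, monitored / unmonitored |
|---|---|---|
| 30%/0.5 vs 30%/0.5 | 0.051, 0.049 | 0 / 0 |
| 40%/0 vs 20%/0 | 0.052, 0.050 | 0 / 0 |
| 40%/0.5 vs 20%/0.5 | 0.051, 0.055 | +1.40 / +1.01 |
| 20%/0.5 vs 35%/0.5 | 0.051, 0.050 | −1.08 / −0.77 |
| 30%/0.5 vs 30%/0.4 | 0.063, 0.056 | −0.76 / +0.33 |
| 30%/0.4 vs 30%/0.5 | 0.060, 0.060 | +0.76 / −0.33 |
| 30%/0.5 vs 30%/0.25, weak link | 0.073, 0.075 | −1.03 / +0.44 |
| 15%/0.5 vs 15%/0.25 | 0.104, 0.095 | −2.58 / +0.46 |
| 30%/0.5 vs 30%/0.25 | 0.132, 0.124 | −1.95 / +0.83 |
| 30%/0.25 vs 30%/0.5 | 0.129, 0.119 | +1.95 / −0.83 |
| 20%/0.5 vs 35%/0.25 | 0.125, 0.119 | −2.84 / +0.18 |
| 30%/0.3 vs 30%/0.6 | 0.162, 0.146 | +2.28 / −0.98 |
| 20%/0.7 vs 35%/0.35 | 0.192, 0.183 | −3.91 / +0.24 |

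The primary test rejects in 4.7–5.5% throughout.

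**Step 6: a version to check by hand.** Let 30% of patients be severe with 30% mortality and the rest have 8.57%, giving 15% overall. Monitor 35% of severe and 30% of other patients in the liberal arm, and 45% and 20% in the restrictive arm.

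- Monitored mortality, liberal: (0.0315 + 0.0180)/0.315 = 15.7%.
- Monitored mortality, restrictive: (0.0405 + 0.0120)/0.275 = 19.1%.
- The contrast is +3.4 points with no treatment effect.

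The log odds ratio of use by severity is 0.23 in one arm and 1.19 in the other, about a five-fold difference. This shows the mechanism. I do not rely on it for size.

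**The case against.** The strongest reply is that the decisive step is undocumented. Protocol 5.3 gives one permission for both arms. Its arm-specific text governs how fluids follow from a result, not whether to monitor. Nothing shows that uptake differs by arm or by prognosis, and if selection is the same in both arms the interaction test keeps its level. Even a difference in amount alone leaves it at 5.0–5.5%. The larger rejection rates need a difference in severity dependence that no passage predicts, and their size is set by the assumptions. All of this stands, and it is why only the possibility of bias is claimed.

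Some textual evidence is also weaker than it looks. Item 9 is missing from protocol 3.6.4, but so is item 11 (enrolment before or after the protocol change), which assignment cannot affect. History of hypertension is not named in SAP 4 either. The wrong section reference is a slip with a clear target. The case report form is not among the documents, so monitoring may have been recorded.

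The SAP's global-null statement does not answer the point. If assignment changed nothing at all, item 9 would be safe. But assignment is meant to change care, and monitoring is part of care. The subgroup contrast can be wrong when assignment alters monitoring and leaves mortality untouched.

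**Conclusion.** The point holds. Item 9 lacks a time window and a rule for 'yes'. Its likeliest reading conditions on care chosen after allocation, and the plan tests it like a baseline factor. Following the SAP as written could give a biased contrast.

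The size and direction are unknown. Under the assumptions shown (no effect on death, 15–40% monitored per arm):

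- Equal selection, or selection unrelated to severity: no bias, rejection 4.9–5.2%.
- Equal severity dependence but different rates: the interaction test is close to nominal (5.0–5.5%), but the contrasts are off by 1.0–1.4 points (monitored) and 0.7–1.0 points (unmonitored).
- A small slope difference: rejection 5.6–6.3%. A two-fold difference with a weak severity–death link: 7.3–7.5%. In both, the monitored contrast is off by 0.7–1.0 points.
- A two-fold slope difference with a stronger link: rejection 9.5–19.2%, monitored contrast off by 1.7–3.9 points in either direction.

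This is one exploratory subgroup and the primary intention-to-treat comparison is untouched. It should be corrected, but it does not threaten the trial's main conclusion. Confidence is medium, because the timing is inferred.

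**What to change.** **Preferred.** Remove item 9 from the treatment-by-subgroup interaction analyses and add to SAP 2.3:

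> To the extent that it was recorded, use of cardiac ultrasound or other haemodynamic monitoring (protocol Section 5.3) will be summarised by arm. No treatment contrast will be made within users or non-users.

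This follows the SAP's own handling of the second litre in the liberal arm. Actual use is a descriptive process metric (SAP 2.3, item 8), and the related subgroup is defined by enrolment period (SAP 3, item 11).

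**Alternative, only if the case report form records timing.** Keep the subgroup but restrict it to monitoring done before randomisation, list the techniques that count and say whether CVP is one, and correct the reference to protocol Section 5.3.

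**Cost.** The preferred change is wording only and asks for no new data; one exploratory contrast is lost. The alternative narrows the contrast and needs the time of use.

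Either way, the sponsor should confirm that use was recorded. It is not listed in protocol 7.1–7.3 or Appendix F, and after the feasibility phase the plan is that "we will perform a simplified data collection of summary fluid and vasopressor administration during the 24-hour treatment period". The nearest documented source is the flow sheet. Protocol 3.6.3 has it record indications for fluids and vasopressors, and under protocol 8.2 "the presence of protocol defined criteria for fluid and vasopressor administration will be collected hourly". That can show that a criterion was met or treatment given, not that monitoring was used, and the criteria differ by arm. If use was not recorded, neither item 9 nor the summary can be produced.

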#### 4. Baseline Characteristics

1. Demographics – Age, Gender, Ethnicity, Race
2. Primary source of infection
3. Co-Morbidities – Charlson, BMI, Pre-hospital level of care
4. Location at time of randomization
5. Illness severity – SOFA (Total and components), mechanical ventilation, ARDS, total pre-randomization fluid input, vasopressor use and infusion rate prior to and at randomization, vital signs, WBC, lactate

#### 5. Statistical Methods

##### Primary Outcome

The primary outcome is intention-to-treat 90-day all cause in-hospital mortality, where in-hospital includes both study and discharge hospitals (i.e. transfer hospitals or LTAC). Subjects who are discharged home (defined as residence prior to admission) prior to day 90 will be assumed to be alive at day 90. Analysis of the primary outcome will be based on the Kaplan Meier day 90 mortality point estimates with all patients who are discharged home or still alive at day 90 censored at day 91, which is beyond the last possible day of death. The day 90 mortality estimates in the two treatment groups will be compared by a Z-test using Greenwood's standard error (Kalbfleisch, J. D. and Prentice, R. L. (1980), *The Statistical Analysis of Failure Time Data*, New York: John Wiley & Sons.).

If there is no loss to follow up then the primary outcome will be compared between treatment groups on the risk difference scale using a generalized linear model with a binomial distribution function and identity link function.

The hypothesis regarding the primary outcome is a two-sided superiority hypothesis.

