1.2 Definitions

Adverse Event: Any untoward medical occurrence associated with the use of a drug or a study procedure, whether or not considered drug related.

Adverse reaction: An adverse reaction means any adverse event caused by a study intervention. An adverse reaction is a subset of all suspected adverse reactions where there is a reason to conclude that the study intervention caused the event.

Assisted Ventilation (or Assisted Breathing): any level of ventilatory support at pressures higher than the unassisted breathing thresholds.

Home: Level of residence or health care facility where the patient was residing prior to hospital admission.

Intention to Treat (ITT): All eligible and consented patients who undergo randomization will be included in the ITT cohort for the purposes of analyzing the primary and secondary study outcomes.

Invasive Mechanical Ventilation: Assisted ventilation delivered by a nasotracheal, orotracheal, or tracheostomy tube.

Legally Authorized Representative: An individual, judicial, or other body authorized under applicable law to consent on behalf of a prospective patient to the patient's participation in the clinical study.

Mortality prior to discharge home before day 90: This primary outcome includes deaths from all causes following randomization in any health care facility prior to discharge home until study day 90. Study subjects still in a health care facility at study day 91 are considered alive for this endpoint.

Funding: National Institutes of Health (National Heart Lung and Blood Institute)

SAEs: Serious Adverse Events Adverse events that are serious and unexpected and have a reasonable possibility that the event was due to a study procedure

Sponsor: The Clinical Coordinating Center at Massachusetts General Hospital

Study day: The day of randomization is study day zero. The next day is study day one etc.

Study hospital: Defined as the hospital where the patient was randomized and enrolled.

Study withdrawal: Defined as permanent withdrawal from study before completion of study activities. If a patient or surrogate requests withdrawal from the study the clinician should seek explicit permission to continue data collection.

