9.1 Sample Size and Stopping Rules for Primary Outcome

The primary outcome is intention-to-treat 90-day all cause in-hospital mortality, where in-hospital includes both study and discharge hospitals (i.e. transfer hospitals or LTAC). Subjects who are discharged home (defined as residence prior to admission) prior to day 90 will be assumed to be alive at day 90.

Sample size is based on a comparison of binomial proportions with an overall two-sided alpha level of 0.05 and power of 0.90. With 15% mortality rate in liberal fluid group and 10.5% mortality rate in the restrictive group, maximum required total sample size is 2320 subjects.

The presumed 15% mortality rate in the liberal fluid group is based on several recently published clinical trials (Process [2], ARISE [3], Promise [4]).

This trial will stop for efficacy of either the restrictive or liberal fluid strategy arm, or futility. The study is designed with a symmetric group sequential t^4 alpha error spending function and a symmetric non-binding t^4 beta error spending function, where t is the information time, defined as the ratio of the effective sample size at the time of the look to the eventual sample size.

We plan to have two interim analyses and one final analysis that will be approximately evenly spaced. However, the scheduling of the DSMB meetings may alter this schedule.

Tables 1 and 2 present the stopping boundaries at each of the two interim analyses if they are equally spaced. The tables present stopping boundaries as either a one-sided p-value or an observed mortality difference. Table 3 presents the probability of stopping at each stage under the null (no effect of fluid) and alternative (restrictive fluid reduces mortality from 15% to 10.5%) hypotheses respectively.

Table 1. Stopping Boundaries: One Sided P Values

Stage	Sample Size	Lower Efficacy	Lower Futility	Upper Futility	Upper Efficacy
1	773	0.0003086	.	.	0.99969
2	1547	0.00479	0.27413	0.72587	0.99521
3	2320	0.02361	0.02361	0.97639	0.97639

Table 2. Stopping Boundaries: Mortality Differences

Stage	Sample Size	Lower Efficacy	Lower Futility	Upper Futility	Upper Efficacy
1	773	-0.08194	.	.	0.08194
2	1547	-0.04384	-0.01016	0.01016	0.04384
3	2320	-0.02742	-0.02742	0.02742	0.02742

Table 3. Cumulative Stopping Probabilities

Stage	Stop: Reject Null Given Null	Stop: Accept Null Given Null	Stop: Reject Null Given Alternative	Stop: Accept Null Given Alternative
1	0.00062	0.00000	0.06136	0.00000
2	0.00988	0.45174	0.52878	0.01919

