## 1.8 Primary Endpoint

The primary outcome is all-cause mortality prior to discharge home before day 90.

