## **2. Endpoints**

### **2.1 Primary Outcome**

The primary outcome is all-cause mortality prior to discharge home before day 90. "Home" is defined as a patient's place of residence prior to enrollment. Thus, if a patient is discharged to a location that is different from the place of residence prior to enrollment (e.g. rehabilitation facility or hospice) then the patient will be followed until they return to their original location, 90 days, or death, whichever comes first.

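### The primary endpoint is defined inconsistently: SAP 5 and Protocol 9.1 limit it to hospital and LTAC deaths, the endpoint definitions do not, and deaths in rehabilitation, hospice or new nursing facilities get contradictory coding

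*SAP*

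**What the plan says.** The headline endpoint, in SAP 1.8 and Protocol 2.8, is broad: "The primary outcome is all-cause mortality prior to discharge home before day 90".

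SAP 2.1, worded the same in Protocol 3.6.1, explains what happens "if a patient is discharged to a location that is different from the place of residence prior to enrollment (e.g. rehabilitation facility or hospice": in that case "the patient will be followed until they return to their original location, 90 days, or death, whichever comes first". Protocol 1.2 defines the same outcome as "deaths from all causes following randomization in any health care facility prior to discharge home until study day 90".

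SAP 5, which specifies the analysis, calls the outcome 90-day in-hospital mortality, "where in-hospital includes both study and discharge hospitals (i.e. transfer hospitals or LTAC". Protocol 9.1, which sets the sample size and stopping boundaries, has the same sentence. SAP 5 then adds two rules about non-events: "Subjects who are discharged home (defined as residence prior to admission) prior to day 90 will be assumed to be alive at day 90", and a Kaplan-Meier estimate with "all patients who are discharged home or still alive at day 90 censored at day 91".

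The objectives and hypotheses (Protocol 2.2, 2.3 and 3.5; SAP 1.2 and 1.3) also speak of in-hospital mortality. The titles of Tables 5 and 6 in Protocol 9.3 use the broad form.

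**The concern.** The in-hospital clause in SAP 5 ends with an i.e., which defines a set rather than giving examples. Rehabilitation, nursing and hospice facilities are not in that set, although SAP 2.1 names two of them and Protocol 1.2 covers all of them. The clause therefore says that a death there is not a primary event, while the censoring rule a few lines later gives no ground for treating it as a non-event.

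This is the primary outcome and the statistic on which the DSMB may stop the trial. Where a patient goes on leaving hospital is decided after randomisation, in a trial that is not blinded. How these deaths are coded should be fixed in the text and not left to whoever programs the analysis.

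**Working it through.** **Step 1: apply each rule to the same patients.** All four lived in their own house before admission.

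| Patient | SAP 2.1 / Protocol 3.6.1 | Protocol 1.2 | SAP 5 in-hospital clause | SAP 5 censoring rule |
|---|---|---|---|---|
| A: to a nursing facility on day 12, dies there on day 40 | event | event | not in-hospital | not censored |
| B: to an inpatient hospice on day 8, dies there on day 10 | event | event | not in-hospital | not censored |
| C: to a relative's house on day 10, dies there on day 30 | event | not in a health care facility | not in-hospital | not censored |
| D: to an LTAC on day 12, dies there on day 40 | event | event | in-hospital | not censored |

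The texts agree only on D. For A, B and C the two parts of SAP 5 conflict with each other. Patient A could be coded as an event on day 40, or censored on day 12, day 40 or day 91, and these need not give the same day-90 Kaplan-Meier estimate. SAP 5 also reserves the binomial identity-link model for the case of no loss to follow-up, so censoring A early could change which test is used.

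C also splits SAP 2.1 from Protocol 1.2. The meaning of home adds to this: Protocol 1.2 refers to a level of residence or facility, SAP 2.1 to the original location. A facility that was the patient's prior residence is home, so the problem concerns only other destinations.

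**Step 2: reproduce the design.** Inputs from Protocol 9.1: 15% versus 10.5%, "overall two-sided alpha level of 0.05 and power of 0.90", total 2320. Allocation is 1:1 (SAP 1.11), so n = 1160 per arm. With d the difference and p̄ the mean of the two rates,

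power = Φ{[d√n − 1.960 √(2p̄(1−p̄))] / √(p1(1−p1) + p2(1−p2))}

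= Φ{[0.045 × 34.059 − 1.960 × √(2 × 0.1275 × 0.8725)] / √(0.1275 + 0.0940)}

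= Φ{(1.5326 − 0.9245) / 0.4706} = Φ(1.292) = 0.902.

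The matching fixed-sample total for 90% power is 2306, against 2320 planned. A simulation of the three-look design with the Table 1 boundaries gives power 0.897 and type I error 0.049 (Table 3: 0.898 and 0.049). The plan's own figures hold.

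**Step 3: illustrate the narrow coding.** The documents give no discharge destinations, so the excluded share s is an assumption. It is taken as equal in both arms, with the excluded deaths treated as non-events and the design's 15% taken to include them. Both rates are multiplied by (1 − s). Expected deaths under the alternative are 1160 × (0.15 + 0.105) = 295.8.

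| s | Rates | Deaths not counted | Fixed-sample power | Group sequential power | Fixed-sample total for 90% |
|---|---|---|---|---|---|
| 0 | 15.0% vs 10.5% | 0 | 0.902 | 0.898 | 2306 |
| 5% | 14.25% vs 9.98% | 14.8 | 0.885 | 0.880 | 2446 |
| 10% | 13.5% vs 9.45% | 29.6 | 0.865 | 0.861 | 2600 |
| 20% | 12.0% vs 8.4% | 59.2 | 0.818 | 0.811 | 2968 |
| 30% | 10.5% vs 7.35% | 88.7 | 0.759 | 0.752 | 3440 |

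For s = 10%: Φ{(0.0405 × 34.059 − 0.8834) / 0.4498} = Φ(1.103) = 0.865. For s = 20%: Φ{(0.036 × 34.059 − 0.8389) / 0.4273} = Φ(0.906) = 0.818.

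Unequal shares would move the estimate itself. Excluding 10% of deaths in the liberal arm only gives 13.5% versus 10.5%, a difference of 3.0 points (power 0.604). Excluding 10% in the restrictive arm only gives 15% versus 9.45%, or 5.55 points.

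**The case against.** A reader might infer that SAP 5 drops these deaths. The documents do not support that. SAP 5 names only two non-event states, and patients A to C are in neither, so an analyst who follows the censoring rule would naturally count an event on the date of death. Nothing tells anyone to recode such a death as survival. The broad endpoint is stated in SAP 1.8 and 2.1, in Protocol 2.8 and 3.6.1, and in the titles of the protocol's own results tables, and no text gives SAP 5 precedence over these. The deaths are also captured: follow-up runs to home, day 90 or death, and 90-day all-cause mortality is a secondary outcome with a national death index check.

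The power figures can be challenged too. The 15% is stated just after the in-hospital clause and rests on cited trials. If it already means hospital mortality only, the narrow reading costs no power. Table 4 also already shows 0.85 at 13% mortality with a 30% relative reduction.

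All of this stands, and it rules out any claim that deaths are lost or that power is known to fall. It does not remove the contradiction. The in-hospital clause still sits in the two sections that govern the analysis and the stopping rule, it says the opposite of the censoring rule for the same patient, and the natural reading is nowhere written down. Nor does it settle deaths at another private address, where Protocol 1.2 and SAP 2.1 part.

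**Conclusion.** The point holds as an inconsistency in the definition of the primary endpoint. Taken literally, the in-hospital clause gives the wrong primary event for a death in a rehabilitation, hospice or new nursing facility, and SAP 5 as a whole gives that death contradictory coding. This follows from the text alone and depends on no assumed figure.

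The numerical effect cannot be determined from the documents. The fall in fixed-sample power from 0.902 to 0.865 or 0.818 is illustrative. It needs three assumptions: that 10% or 20% of deaths in each arm occur in such places, that they are coded as non-events, and that the design's 15% includes them. A reader might also infer bias between arms. Nothing in the documents indicates that discharge destination differs by arm, and any endpoint that ends at discharge home depends on discharge to some degree. The unequal-share figures show only why the rule should be settled before outcomes are compared by arm.

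**What to change.** In SAP 5 and Protocol 9.1, replace the in-hospital clause with the SAP 2.1 rule. Suggested content: any death through the day-90 limit that occurs before first return to the pre-enrollment residence is an event at its date, whatever the facility; only patients discharged to that residence, or alive at day 90, are censored at day 91.

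Align Protocol 1.2 to the same sentence, including its definition of home and an explicit decision on deaths at other private addresses. SAP 2.1 as written counts them. Bring the in-hospital mortality wording in Protocol 2.2, 2.3 and 3.5 and in SAP 1.2 and 1.3 into line.

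The cost is wording, plus one check of the data. SAP 2.1 already requires the follow-up, and Appendix F schedules vital status at day 90. As the table reads, however, Appendix F schedules disposition only at day 28, so the sponsor should confirm that dates of return home between day 28 and day 90 are recorded.
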